8.7 Treatment of Overdose

There is no experience with OPC-167832 overdose in humans, refer to the IB. For itraconazole and carbamazepine, refer to USPIs

8.8 Subject Assessment Recording

Not applicable.

8.9 Other Assessments

Not applicable.

9 Statistical Considerations

9.1 Sample Size

Sample size was selected assuming an intra-subject coefficient of variation for AUC of 25%, such that the point estimate of the ratio of geometric means for the PK parameters of OPC-167832 with and without coadministration of the perpetrator (itraconazole or carbamazepine) will fall within 83% and 120% of the true value with 90% confidence.

Twenty-four subjects will be enrolled, 12 subjects in each part, to target approximately 10 healthy male or female subjects complete each trial part.

9.2 Datasets for Analysis

The safety dataset includes all subjects who receive at least 1 dose of IMP.

The PK dataset will consist of all subjects who receive at least 1 dose of IMP and have at least 1 postdose evaluable plasma concentration.

9.3 Handling of Missing Data for Primary and Secondary Endpoint Analysis

No data imputation will be performed for missing PK and safety data in this trial.

9.4 Statistical Analyses

9.4.1 Primary Endpoint(s) Analysis

The effect of itraconazole or carbamazepine administration on the single-dose PK of OPC-167832 will be assessed using the primary PK parameters of OPC-167832: C_{max} , AUC calculated to the last observable concentration at time t (AUC_t), and AUC from time zero to infinity (AUC_{∞}) in the presence and absence of either itraconazole or carbamazepine.

Statistical analyses will be performed using the log-transformed PK parameters. The magnitude of the DDI will be assessed by computing the ratio of the geometric means of OPC-167832 + potentially interacting drug versus OPC-167832 alone and the corresponding 90% confidence intervals (CIs) based on the log-transformed data.

An analysis of variance will be performed on the log-transformed PK parameters C_{max} , AUC_t , and AUC_{∞} for OPC-167832 and/or its metabolites using the MIXED procedure in SAS for each part separately. The mixed-effects linear model for each PK parameter will include treatment (OPC-167832 + potentially interacting drug [test] and OPC-167832 alone [reference]) as a fixed effect and subject as a random effect. From each analysis,

mean differences between the treatments OPC-167832 + potentially interacting drug and OPC-167832 alone and the 90% CI for the differences will be derived. The antilog of the differences will then provide an estimate of the geometric mean ratios (GMR; OPC-167832 + potentially interacting drug/OPC-167832 alone), and the antilog of the confidence limits will provide the 90% CIs for the GMRs.

9.4.2 Control of Experiment-wise Type 1 Error

Not applicable.

9.4.3 Safety Analyses

The safety analysis will be conducted on the safety dataset for Part 1 and Part 2, separately. Safety variables to be analyzed include AEs, clinical laboratory tests, vital signs, ECGs, physical examinations, and the C-SSRS. Summaries will be based upon subjects who took at least 1 dose of IMP. The treatment group refers to OPC-167832 alone and OPC-167832 + itraconazole/carbamazepine. Baseline will be the last available predose value at the start of the treatment period, unless otherwise defined in the statistical analysis plan.

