4.1 Type/Design of Trial

This is a single-center, 2-part, open-label DDI trial in healthy adult subjects. Part 1 and Part 2 will have fixed sequence designs with 12 subjects in each part for a total of 24 subjects enrolled.

- Part 1: OPC-167832 + itraconazole (strong CYP3A inhibitor)
- Part 2: OPC-167832 + carbamazepine (strong CYP3A inducer)

Following a screening period of up to 28 days, eligible subjects will enter the clinic on the day prior to the first treatment day (Day -1).

For Part 1, the impact of CYP3A inhibition on the PK of OPC-167832 will be assessed. Subjects will receive a single, 30-mg, oral dose of OPC-167832 **CCI** in the fasted state on Day 1 with blood collections for PK assessment of OPC-167832 from Day 1 through Day 8. On Day 8, subjects will receive 200-mg doses of itraconazole in the morning and evening (200 mg twice daily [BID]) followed by 200 mg of itraconazole administered QD on Day 9 through Day 14 to approach steady-state conditions for itraconazole. On Day 15, a single, 30-mg, oral dose of OPC-167832 **CCI** will

be administered concurrently with a 200-mg dose of itraconazole in the fasted state with blood collections for PK assessment of OPC-167832 from Day 15 through Day 26. Once daily 200-mg doses of itraconazole will continue to be administered on Day 16 through Day 25. Subjects will be discharged from the clinic after the PK sample on Day 26 or early termination (ET).

For Part 2, the impact of CYP3A induction on the PK of OPC-167832 will be assessed. Subjects will receive a single, 30-mg, oral dose of OPC-167832 CCI on Day 1 in the fasted state with blood collections for PK assessment of OPC-167832 from Day 1 through Day 8. On Day 8 through Day 10, subjects will receive 100 mg BID carbamazepine followed by 200 mg BID carbamazepine administration on Day 11 through Day 13 and 300 mg BID carbamazepine administration on Day 14 through Day 31. On Day 25, a 30-mg oral dose of OPC-167832 CCI will be administered concurrently with the morning 300 mg dose of carbamazepine in the fasted state with blood collections for PK assessment of OPC-167832 from Day 25 through Day 32. Subjects will be discharged from the clinic after the PK sample on Day 32 or ET.

All subjects will be contacted by phone 30 days after the last dose of OPC-167832 to assess any new or ongoing AEs and to record concomitant medications.

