9.4.3.1 Adverse Events

All AEs will be coded by system organ class and Medical Dictionary for Regulatory Activities (MedDRA) preferred term. The incidence of the following events will be summarized by treatment group:

- Treatment-emergent AEs
- TEAEs by severity
- TEAEs with an outcome of death
- Serious TEAEs
- TEAEs leading to discontinuation of the IMP

The same summaries will be prepared for TEAEs causally related to the IMP.

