9.4.3.2 Clinical Laboratory Data

Descriptive statistics will be used to summarize the change from baseline for laboratory tests by treatment group for each visit. Baseline is defined as the last nonmissing value obtained at a scheduled visit on or before Day -1. If the Day -1 measurement is missing, the baseline value will be the last nonmissing measurement from the screening visit (the previous scheduled visit). The incidence of potentially clinically significant changes and abnormalities in clinical laboratory test parameters will be summarized by treatment group. Clinical laboratory test data will be presented in listings.

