10.2 Adverse Events

All AEs will be coded by Medical Dictionary for Regulatory Activities (MedDRA, Version 25 or a later version if available).

Treatment-emergent adverse events (TEAEs) are defined as AEs with an onset date on or after the start of IMP treatment. TEAEs are all AEs which started after the start of IMP treatment; or if the event was continuous from baseline and worsens either in intensity or frequency, becomes serious, is assessed as IMP-related or results in death.

Relatedness of AEs to IMP will be collected for each IMP, individually, OPC 167832 and itraconazole for Part 1 and OPC 167832 and carbamazepine for Part 2.

A Serious Adverse Event (SAE) includes any event that results in any of the following outcomes:

- Death.
- Life-threatening; ie, the subject was, in the opinion of the investigator, at immediate risk of death from the event as it occurred. It does not include an event that, had it occurred in a more severe form, might have caused death.
- Persistent or significant incapacity/disability or substantial disruption of the ability to conduct normal life functions.
- Requires inpatient hospitalization or prolongs hospitalization.
Hospitalization itself should not be reported as an SAE; whenever possible the reason for the hospitalization should be reported.
 - Hospitalizations or prolonged hospitalizations for social admissions (ie, those required for reasons of convenience or other nonmedical need) are not considered SAEs.
 - Prescheduled hospitalization to address a condition that has existed prior to the signing of the ICF should not be considered an SAE and should be recorded as medical history.
- Congenital anomaly/birth defect.

Quabodepistat (OPC-167832)

Study 323-201-00007

- Other medically significant events that, based upon appropriate medical judgment, may jeopardize the subject and may require medical or surgical intervention to prevent one of the outcomes listed above, eg, allergic bronchospasm requiring intensive treatment in an emergency room or home, blood dyscrasias or convulsions that do not result in hospitalization, or the development of drug dependency or drug abuse.

Nonserious AEs are all AEs that do not meet the criteria for a “serious” AE.

The frequency and percentage of subjects with the following events, together with the number of events, (events listed below), will be summarized by SOC, MedDRA preferred term, severity, and treatment for each of Part 1 and Part 2 separately

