10.7 Suicidality Monitoring

Suicidality monitoring will be conducted only in subjects enrolled in Part 2 and at the time points described in the SoA ([Table 1.3-2 of the protocol](#)).

The “Baseline/Screening” version of the C-SSRS will be completed at screening. This will be the baseline assessment for the C-SSRS.

The “Since Last Visit” version will be completed at all other specified visits (including ET, if applicable).

The “Baseline/Screening” version be used to assess Suicidal Ideation and Suicidal Behavior in both the subjects' lifetime and within the past 12 months prior to screening. There are a maximum of 19 items to be completed: 7 required, 10 potential additional items if there is a positive response to a required item, and 2 items for suicide/suicide behavior present during the interview. The C-SSRS uses dichotomous scales (ie, yes or no), Likert scales, and text or narrative to further describe the thoughts or behaviors.

The C-SSRS data will be analyzed for evidence of any treatment-emergent issues related to suicidal ideation or behavior. The incidence of suicidality, suicidal behavior, and

Quabodepistat (OPC-167832)

Study 323-201-00007

suicidal ideation will be summarized by treatment group and visit. No inferential statistical analyses will be performed. C-SSRS data will be listed.

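### Safety is tabulated in two treatment groups although each subject passes through three dosing phases, so adverse events starting on itraconazole or carbamazepine before the second OPC-167832 dose have no correct column

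*Protocol*

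**What the plan says.** Protocol 9.4.3 fixes the grouping for all safety summaries: "The treatment group refers to OPC-167832 alone and OPC-167832 + itraconazole/carbamazepine". Protocol 9.4.3.1 applies it to adverse events: "The incidence of the following events will be summarized by treatment group". The list that follows includes events leading to discontinuation of the IMP. Protocol 9.4.3.2 will "summarize the change from baseline for laboratory tests by treatment group for each visit", and summarises the incidence of potentially clinically significant laboratory changes by treatment group, with no mention of visit.

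In SAP 10.2 the adverse event counts "will be summarized by SOC, MedDRA preferred term, severity, and treatment for each of Part 1 and Part 2 separately". The SAP does not list the levels of treatment for safety. The only levels it names are in the PK model code of Appendix 6, two per part. SAP section 15 reports no changes to the planned analysis, so nothing replaces the Protocol's two groups.

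The dosing in Protocol 4.1 has three phases. In Part 1, "On Day 8, subjects will receive 200-mg doses of itraconazole in the morning and evening", "followed by 200 mg of itraconazole administered QD on Day 9 through Day 14", and the second OPC-167832 dose comes on Day 15. In Part 2, "On Day 8 through Day 10, subjects will receive 100 mg BID carbamazepine followed by 200 mg BID carbamazepine" from Day 11 and 300 mg BID from Day 14, with the second OPC-167832 dose on Day 25.

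**The concern.** The secondary objective is the safety of OPC-167832 given alone or with each interacting drug. The tables that answer it have a column for each of those two states and none for the stretch between them, when the subject takes itraconazole or carbamazepine and no new OPC-167832. No text assigns events by onset date.

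There are three possible outcomes. Counting these events under the combination reports events that began before the combination was given. Counting them under OPC-167832 alone attaches events on the interacting drug to the study drug. Dropping them loses them from the summary. The choice would be made by the programmer, in an open-label trial, possibly after the data have been seen.

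Part 2 matters most. Protocol 4.3 justifies the carbamazepine titration by tolerability and drop-out, and a footnote to Table 1.3-2 anticipates carbamazepine-related events, so the unassigned phase is one where the Protocol itself expects events.

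**Working it through.** **Inputs.** Dosing days: Protocol 4.1 and Table 6.1-1. In-clinic durations and follow-up days: Protocol 1.1. Assessment times: Tables 1.3-1 and 1.3-2 with footnotes.

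**Check of day counting.** With no Day 0, Day -1 plus Days 1-26 is 1 + 26 = 27 days, and Day -1 plus Days 1-32 is 1 + 32 = 33 days. Both match the Protocol. Follow-up at 30 days after the second dose gives 15 + 30 = Day 45 and 25 + 30 = Day 55, which also match.

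**Phase lengths, first dose to discharge.**

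| Phase | Part 1 | Part 2 |
|---|---|---|
| OPC-167832 alone | Days 1-7: 7 | Days 1-7: 7 |
| Interacting drug, no new OPC-167832 | Days 8-14: 7 | Days 8-24: 17 |
| Combination | Days 15-26: 12 | Days 25-32: 8 |
| Total | 26 | 32 |

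**Share of time in the middle phase.**
- Of interacting-drug dosing days (Days 8-25 = 18; Days 8-31 = 24): 7/18 = 39%; 17/24 = 71%.
- Of days from first dose to discharge: 7/26 = 27%; 17/32 = 53%.
- If pooled with the combination, as a share of that column's in-clinic time: 7/(7 + 12) = 37%; 17/(17 + 8) = 68%.
- The same with the combination run to the follow-up call (Days 15-45 and 25-55, 31 days each): 7/38 = 18%; 17/48 = 35%.
- If pooled with OPC-167832 alone: 7/(7 + 7) = 50%; 17/(7 + 17) = 71%.

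**Titration.** Carbamazepine is below 300 mg BID on Days 8-13. All six of those days fall in the middle phase.

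**Scheduled assessments after the first carbamazepine dose (Part 2).**
- Laboratory: Days 11, 14, 25 predose and 32. Three of the four precede the second OPC-167832 dose.
- ECG: Day 8 at 6 h, Day 9, Day 14 predose, Day 14 at 6 h, Day 15, Day 25 predose, Day 25 at 3 h, Day 26 and Day 32. Six of the nine precede it.

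**Part 1.** No laboratory, vital-sign or ECG assessment is scheduled on Days 8-14. Apart from adverse events, only values taken on Day 15 before the second dose are affected.

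**Denominator.** With 12 subjects per part, moving one subject changes a percentage by 1/12 = 8 points and moving two by 2/12 = 17 points. A subject who stops on Days 8-24 of Part 2 never receives the combination, yet discontinuations are tabulated in the two groups only.

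**The case against.** The strongest reply is that the plan already separates the drugs. SAP 6.4 counts itraconazole and carbamazepine as IMP. SAP 10.2 collects relatedness for each drug individually, plans separate tables of events related to OPC-167832, to itraconazole and to carbamazepine, and lists all adverse events by part. Onset dates are recorded, so phase can be recovered. This stands in part. Relatedness is an open-label investigator judgement, and those tables are split by the same undefined treatment variable. They do not give a count by phase, and listings preserve the data without supplying the summary.

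For laboratory and ECG means the reply is stronger. The Protocol's change-from-baseline summaries are by group and visit, and SAP 10.6 summarises ECG by part and time point. Day 9, 11, 14, 15 and Day 25 predose values stay visible as such, so the counts of 3 of 4 draws and 6 of 9 ECGs show exposure to the problem and are not counts of errors. The explicit by-group exposure is the laboratory abnormality incidence in Protocol 9.4.3.2.

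A reader might infer that all events of the middle phase are credited to one of the two named groups, probably the combination, because the schedules appear to start Period 2 on Day 8. The documents do not support this. Period 2 is a schedule heading, and no analysis text assigns events by period. The Part 2 code in Appendix 6 has three coefficients for two named levels, which may hint at a third level but defines none.

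SAP 10.7 says "suicidal ideation will be summarized by treatment group and visit", which might suggest the same fault in the C-SSRS. The only scheduled C-SSRS after dosing starts is at Day 32 or early termination, on the form covering the time since the last visit. It looks back to Day -1 across the phases the subject has been through and cannot be placed in one of them.

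**Conclusion.** The point holds as an undefined allocation with no correct option available, and it should be fixed. The unassigned phase is 7 of 18 itraconazole days (39%) and 17 of 24 carbamazepine days (71%). It matters mainly for the adverse event tables and the by-group laboratory abnormality incidence, and more in Part 2 than in Part 1.

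Two stronger readings go too far. The 71% is a share of dosing days; it would be a share of events only under a constant daily event rate, which the documents do not support across a dose titration. Nor is the safety reporting uninterpretable: it is descriptive, with no planned test between groups, and the drug-specific tables and by-visit summaries carry part of the information.

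The middle phase means no new OPC-167832 dose. Residual drug from Day 1 may persist, and since the half-life is redacted this cannot be checked. Sample size and the primary PK analysis are unaffected.

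**What to change.** In Protocol 9.4.3 and SAP section 10, define the same three safety phases for each part:

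1. OPC-167832 alone: from the first OPC-167832 dose to just before the first Day 8 dose of itraconazole or carbamazepine.
2. Interacting drug with no new OPC-167832 dose: from that Day 8 dose to just before the second OPC-167832 dose, including predose values on Day 15 (Part 1) or Day 25 (Part 2).
3. Combination: from the second OPC-167832 dose to last contact.

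Assign adverse events by onset date, and by time where recorded. Protocol 8.6.2 asks for times only where possible, so state a tie rule for Days 8, 15 and 25 when the time is missing. Use as denominator the subjects dosed in each phase. Apply the same windows to the incidence of laboratory, vital-sign and ECG abnormalities. Table 1.3-1 gives no clock time for the Part 1 laboratory draw on Day 15, so assign it by its actual time. Report the Day 32 or early-termination C-SSRS as covering the whole treatment period.

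The cost is wording in two documents and one more column per safety table, with smaller counts in each. No added assessments are needed. A footnote should say that phase 2 may include residual OPC-167832 from Day 1.

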9.4.3.1 Adverse Events

All AEs will be coded by system organ class and Medical Dictionary for Regulatory Activities (MedDRA) preferred term. The incidence of the following events will be summarized by treatment group:

- Treatment-emergent AEs
- TEAEs by severity
- TEAEs with an outcome of death
- Serious TEAEs
- TEAEs leading to discontinuation of the IMP

The same summaries will be prepared for TEAEs causally related to the IMP.

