An analysis of variance will be performed on the log-transformed PK parameters C_{\max} , AUC_t , and AUC_{∞} for OPC-167832 and/or its metabolites using the MIXED procedure in SAS for each part separately. The mixed-effects linear model for each PK parameter will include treatment (OPC-167832 + potentially interacting drug [test] and OPC-167832 alone [reference]) as a fixed effect and subject as a random effect. From each analysis, mean differences between the treatments OPC-167832 + potentially interacting drug and OPC-167832 alone and the 90% CI for the differences will be derived. The antilog of the differences will then provide an estimate of the geometric mean ratios (GMR; OPC-167832 + potentially interacting drug/OPC-167832 alone), and the antilog of the confidence limits will provide the 90% CIs for the GMRs.

Trial Duration: Each subject in this trial is expected to participate in the following periods of the trial (approximate durations listed):

- Eligibility screening period: Day –28 to Day –2
- In-clinic treatment (2 dosing periods):
 - Part 1: Day –1 to Day 26 days (27 days)
 - OR
 - Part 2: Day –1 to Day 32 (33 days)
- Safety follow-up phone call: 30 (+ 2) days after the last dose of OPC-167832 (eg, Day 45 [+ 2 days] for Part 1 and Day 55 [+ 2 days] for Part 2 for trial completers).

The trial start is defined as the date the first subject signs their informed consent form. Overall, the trial duration, from signing of the first subject's informed consent form to the last subject's final assessment, is expected to be approximately 11 weeks for Part 1 and approximately 12 weeks for Part 2.

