8.6 Adverse Events

8.6.1 Definitions

Trial interventions are all pre-specified, investigational and noninvestigational medicinal products, intended to be administered to the subjects during the conduct of the trial.

Adverse Event: An AE is defined as any untoward medical occurrence in a clinical trial subject administered a trial intervention and which does not necessarily have a causal relationship with this intervention. Adverse events would not include information recorded as medical history at screening for pre-planned procedures for which the underlying condition was known and no worsening occurred. An adverse reaction is any untoward and unintended response to a trial intervention related to any dose administered.

A suspected adverse reaction is any AE for which there is a reasonable possibility that the trial intervention caused the AE. For the purpose of Investigational New Drug (IND) safety reporting, “reasonable possibility” means there is evidence to suggest a causal relationship between the trial intervention and the AE. Suspected adverse reaction implies a lesser degree of certainty about causality.

Treatment-emergent AEs (TEAEs) are defined as AEs with an onset date on or after the start of IMP treatment. In more detail, TEAEs are all AEs which started after the start of IMP; or if the event was continuous from baseline and worsens either in intensity or frequency, becomes serious, is assessed as IMP-related or results in death.

A Serious Adverse Event (SAE) includes any event that results in any of the following outcomes:

- Death.
- Life-threatening; ie, the subject was, in the opinion of the investigator, at immediate risk of death from the event as it occurred. It does not include an event that, had it occurred in a more severe form, might have caused death.
- Persistent or significant incapacity/disability or substantial disruption of the ability to conduct normal life functions.
- Requires inpatient hospitalization or prolongs hospitalization.
- Hospitalization itself should not be reported as an SAE; whenever possible the reason for the hospitalization should be reported.
 - Hospitalizations or prolonged hospitalizations for social admissions (ie, those required for reasons of convenience or other nonmedical need) are not considered SAEs.
 - Prescheduled hospitalization to address a condition that has existed prior to the signing of the ICF should not be considered an SAE and should be recorded as medical history.

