8.6.2 Eliciting and Reporting Adverse Events

The investigator will regularly assess subjects for the occurrence of AEs. To avoid bias in eliciting AEs, subjects should be asked the nonleading question: "How have you felt since your last visit?" All AEs (serious and nonserious) reported by the subject must be

recorded on the source documents and eCRF provided by the sponsor. Adverse event collection will begin after a subject, or parent/legal guardian, signs the ICF, and will continue until the 30-day follow-up phone call. All AEs must be reported after subject informed consent/assent has been obtained, including screening failures due to AEs, irrespective of trial intervention administration.

Medical terminology should be used for AE reporting. Adverse events should be reported as a single unifying diagnosis whenever possible or, in the absence of a unifying diagnosis, as individual signs or symptoms.

Exacerbation or disease progression should be reported as an AE only if there are unusual or severe clinical features that were not present, or experienced earlier, or not expected based on the course of the condition.

Medical or surgical procedures (eg, endoscopy, appendectomy) should not be reported as AEs; however, the condition that led to the procedure may be reported as an AE.

If a reported AE undergoes a change or worsening in severity, seriousness, or toxicity, it should be reported as a new AE in the eCRF.

In addition, the sponsor must be notified immediately by telephone, fax, or e-mail of any IREs according to the procedure outlined below, in [Section 8.6.3](#). Special attention should be paid to recording hospitalization and concomitant medications.

The AE, start date, end date (if possible, start date and time, end date and time), seriousness, severity, relationship to IMP (causality), action taken with IMP, and outcome will be recorded on the source documents and in the eCRF.

Note: Start time should be recorded in the event an AE such as vomiting occurs. When capturing start/end time, at a minimum, the hour should be captured in the event it is difficult to specify in hours and minutes.

Regarding SAE, relationship to, and action taken with trial intervention(s) other than IMP will also be evaluated per each intervention. These evaluations will be recorded in the source documents and in the eCRF and will be reported using the IRE form (see [Section 8.6.3](#)).

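### AE incidence is tabulated by treatment with no rule assigning events to a treatment and no allowance for unequal time at risk

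*Protocol*

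**What the plan says.** Protocol 9.4.3.1 introduces its list of AE tables with "The incidence of the following events will be summarized by treatment group". Protocol 9.4.3 defines the groups: "The treatment group refers to OPC-167832 alone and OPC-167832 + itraconazole/carbamazepine". There is no group for the interacting drug alone. SAP 10.2 asks for the frequency and percentage of subjects, with the number of events, "summarized by SOC, MedDRA preferred term, severity, and treatment for each of Part 1 and Part 2 separately".

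The time frame comes from other sections:

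- Protocol 8.6.1 gives the definition: "Treatment-emergent AEs (TEAEs) are defined as AEs with an onset date on or after the start of IMP treatment". It has a start, but no end and no link to a particular treatment. SAP 10.2 uses the same definition.
- Protocol 8.6.2 has AE collection begin at consent and "continue until the 30-day follow-up phone call".
- The Synopsis (Trial Duration) puts that call at "30 (+ 2) days after the last dose of OPC-167832 (eg, Day 45 [+ 2 days] for Part 1 and Day 55 [+ 2 days] for Part 2" among completers.
- Protocol 4.1 and Table 6.1-1 give OPC-167832 on Day 1, start the interacting drug on Day 8 in both parts, and give the second OPC-167832 dose on Day 15 (Part 1) or Day 25 (Part 2).

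SAP 10.1 summarizes extent of exposure, but nothing connects it to the AE tables. Neither document mentions a time-at-risk denominator, a common window or a separate follow-up column.

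**The concern.** A percentage of subjects with at least one AE rises with the length of observation, even if the drug does nothing. The two columns cover different lengths of time, and the programmer must decide how different, because no rule places AEs that start on Days 8-14 (Part 1) or Days 8-24 (Part 2). Those days are on the interacting drug only, and in Part 2 they include the carbamazepine titration.

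The secondary objective is the safety and tolerability of OPC-167832 alone or in combination, and these columns are its main AE display. Protocol 4.3 allows for OPC-167832 exposure about 5 to 6 times higher with itraconazole. Readers will therefore look for more AEs on the combination in Part 1, and longer observation produces the same pattern.

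**Working it through.** **Check of the stated days.** Second OPC-167832 dose plus 30 days: 15 + 30 = Day 45 and 25 + 30 = Day 55. Both match the Synopsis.

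**Window lengths.**

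- OPC-167832 before any interacting drug: 8 − 1 = 7 days, both parts.
- Interacting drug only: 15 − 8 = 7 days (Part 1); 25 − 8 = 17 days (Part 2).
- After the combination dose, to the call: 45 − 15 = 30 days; 55 − 25 = 30 days.
- After the combination dose, in clinic only: 26 − 15 = 11 days; 32 − 25 = 7 days.

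**Three readings that the text allows**, according to where AEs from the interacting-drug-only days go:

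- A: in neither column.
- B: with the last OPC-167832 dose given. The alone window becomes 7 + 7 = 14 days (Part 1) or 7 + 17 = 24 days (Part 2).
- C: in the combination column. That window becomes 7 + 30 = 37 days (Part 1) or 17 + 30 = 47 days (Part 2).

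**Effect on incidence with no drug effect.** The documents give no AE rate, so one is assumed. Let p be the probability of at least one AE in 7 days, with the same constant rate throughout. Over T days:

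incidence = 1 − (1 − p)^(T/7)

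With p = 10%:

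| Reading | Part | Alone v combination (days) | Window ratio | Expected incidence | Incidence ratio |
|---|---|---|---|---|---|
| A | 1 and 2 | 7 v 30 | 4.29 | 10.0% v 36.3% | 3.63 |
| B | 1 | 14 v 30 | 2.14 | 19.0% v 36.3% | 1.91 |
| B | 2 | 24 v 30 | 1.25 | 30.3% v 36.3% | 1.20 |
| C | 1 | 7 v 37 | 5.29 | 10.0% v 42.7% | 4.27 |
| C | 2 | 7 v 47 | 6.71 | 10.0% v 50.7% | 5.07 |

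Under reading A this is 1.2 v 4.4 of 12 subjects.

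**Sensitivity to the assumed rate (reading A).** For p = 5%, 20%, 30% and 50%, the 30-day incidence is 19.7%, 61.6%, 78.3% and 94.9%, so the ratios are 3.95, 3.08, 2.61 and 1.90.

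**Sensitivity to timing (reading A).** Suppose a fraction q of subjects also has an acute AE within 7 days of each OPC-167832 dose, equally under both treatments. Then incidence = 1 − (1 − q)(1 − p)^(T/7). With p = 10%, q = 20% gives 28.0% v 49.1% (ratio 1.75), and q = 40% gives 46.0% v 61.8% (ratio 1.34).

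**In-clinic days only, interacting-drug-only days left out.** Part 1 is 7 v 11 days: 10.0% v 15.3%, ratio 1.53. Part 2 is 7 v 7 days: ratio 1.00.

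**After correction.** With 7 days in each column, equal rates give a ratio of 1.00. Events per subject-day also have an expected ratio of 1.00 when rates are equal, whatever the window lengths.

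**The case against.** Several points stand against a stronger version of this concern.

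- A reader might infer that AE collection stops 7 days after OPC-167832 alone. It does not. Collection is continuous, and 7 days is only the time before the interacting drug starts.
- A reader might take 7 v 30 days as the plan's own split. It is one reading of several. Under reading B in Part 2 the window ratio is only 1.25.
- A reader might infer a planned comparison. Both documents say the AEs are summarized. Safety statistics are descriptive, type 1 error control does not apply (Protocol 9.4.2), and the sample size rests on PK precision.
- The incidence ratios depend on an assumed constant rate. They shrink if AEs cluster after dosing. After discharge, AEs depend on one call covering 45 − 26 = 19 or 55 − 32 = 23 days, so recording may fall below the in-clinic rate.
- The SAP offers partial safeguards: relatedness is collected for each drug, with tables by drug; event counts accompany percentages; exposure is summarized; all AEs are listed, and onset dates are recorded.

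These points limit the size and certainty of the distortion. They do not supply an assignment rule or a denominator, and side-by-side percentages can mislead without any test. Relatedness in an open-label trial is a judgement and does not equalize observation time.

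**Conclusion.** The point holds as a gap in the AE tabulation rules with a predictable direction. Whenever AEs are followed to the call, the combination column has more time at risk under all three readings, so background AEs raise its percentage. The window ratio is 1.25 to 6.7, depending on a choice that neither document makes. At an assumed 10% per 7 days the incidence ratio is 1.20 to 5.07; other rates or early clustering change it.

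The documents do not support a claim that the combination will look worse by a fixed factor. Nor does the direction hold without follow-up to the call. Counting in-clinic days only, Part 2 has no imbalance if the interacting-drug-only days are left out. If those days go with the last OPC-167832 dose, the imbalance reverses (14 v 11 days in Part 1, 24 v 7 in Part 2). That is a further reason to fix the rule in advance. The primary PK analysis is unaffected.

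**What to change.** In SAP 10.2, assign each TEAE by onset to one of four columns:

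1. OPC-167832 alone: Day 1 to the first interacting-drug dose.
2. Interacting drug alone: Day 8 to the second OPC-167832 dose.
3. Combination: second OPC-167832 dose to the end of in-clinic observation (Day 26 in Part 1, Day 32 in Part 2). This keeps Part 1 AEs that start while itraconazole continues to Day 25 in the combination column.
4. Post-discharge follow-up: from then to the call.

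Show subject-days and events per subject-day for each column. State how an AE that starts on a boundary day without a recorded time is placed, since Protocol 8.6.2 asks for times only where possible.

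Add one display of incidence within 0-168 h after each OPC-167832 dose, so that both windows are 7 days. Keep the all-time table so that later Part 1 events are not lost. State beside the display that equal windows do not remove period effects of the fixed sequence or the interacting drug's own AEs.

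The cost is SAP wording and one extra table per part, from data already collected. The downside is that the equal-window display will contain few events with 12 subjects per part.
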